In pregnant women with 2nd trimester missed abortion with previous caesarean section , does Ulipristal Acetate decrease the time interval to achieve abortion when combined with Misoprostol in comparison to Misoprostol alone?

Hypothesis

In pregnant women with 2nd trimester missed abortion with previous caesarean section , Ulipristal Acetate may decrease the time interval to achieve abortion when combined with Misoprostol in comparison to misoprostol alone.

Study Design

Type of Study: A Randomized Controlled Trial.

Study Setting: Ain Shams University Maternity Hospital.

Study Period: Starting from January 2019 to January 2020.

Participants

Study Population: Women with 2nd trimester missed abortion with previous caesarean section undergoing medication abortion attending either outpatient clinic or emergency room

Eligibility Criteria:

Inclusion Criteria:

- Women with 2nd trimester missed abortions
- Gestational age 13-26 weeks.
- Women with a previous caesarian section scar,(Para-1CS till Para-4CS).
- Women counseled and chose medication abortion rather than surgical evacuation

Exclusion Criteria:

- Women with an accompanying medical disorder such as: Preeclampsia, DM or Heart disease.
- Primigravida women or non scarred uterus.
- Women with previous myomectomy or hysterotomy scar or upper segment caesarean section scar.

- Induction of abortion in women with congenital fetal malformations or positive fetal pulsations due to medical disorder
- Women with placenta previa.
- Allergy or contraindications to either Ulipristal acetate or Misoprostol.
- Women with inevitable abortion in the form of vaginal bleeding or uterine contractions.

All women who met the inclusion criteria will be assessed.

This assessment will include:

Detailed History:

Personal history (Maternal age, weight, height).

Obstetric history . Gravidity, Parity, previous operative delivery.

Any associated complication during pregnancy.

Menstrual history (Last menstrual period).

Maternal medical history (Hypertension & Coagulopathies).

Physical Examination:

- General examination:** a. Vital signs b. Chest and heart examination
- Abdominal examination:** a. Gestational age b. Fetal weight, amount of liquor, fetal lie and presentation, fetal heart sounds c. Uterine contractions and scar of previous surgeries
- Vaginal examination** to detect cervical dilatation, consistency, position and length.

Investigations:

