CBC, Liver Function, Kidney function, Random blood sugar, Prothrombin time (PT)

Obstetric ultrasound study: For assessment of gestational age, fetal life, implantation site of the placenta and fetal weight.

Interventions

The study sample, will be divided into two groups as follows:

Group A: will receive Ulipristal acetate 30mg, starting misoprostol 12 hours later 100µg every 6 hours buccal according to FIGO guidelines 2017.

Group B: will receive placebo tablet then 12 hours later start misoprostol 100µg every 6 hours buccal according to FIGO guidelines 2017.

Then women in both groups will have rest for 24hours after 5 doses of misoprostol

and restart misoprostol-only in both groups with the same above regimens, repeating the same sequence for two weeks unless there is excessive bleeding or infection. If failed, patient will proceed to hysterotomy.

Primary outcome

1. Induction-to-abortion interval time.

Secondary outcome

1. Success rate for complete evacuation between both groups.
2. Occurrence of side effects: i) Nausea ii) Vomiting iii) Fever iv) Pain, between both groups.
3. Rate of uterine rupture between both groups.

4. Amount of blood loss, as a comparison between both groups.
5. Rate of hysterotomy between both groups.

Sampling Method:

Sample Size: A pilot sample was used primarily, to accurately calculate the main study sample. According to Julious SA. ⁽⁶⁾, a pilot sample size of 24 (12 per arm) was used. The objective is not to prove superiority of the treatment but to test trial procedures and processes and to get estimates of parameters for the main trial sample size calculation. Women fulfilling the inclusion criteria and consenting were randomly assigned to either group

Randomization, Allocation and Concealment:

A computer generated list via MedCalc® Software, version 13.2.2 will be used for randomization, assigning each participant number to either study group using sequentially numbered, otherwise identical, sealed envelopes (SNOSE), each

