containing a 2-inch by 2-inch paper with a written code designating the assigned group. These papers were placed in a folded sheet of aluminum foil fitted inside the envelope. To ensure concealment, efforts will be taken to assure absence of any detectable differences in size or weight between intervention and control envelopes. Envelopes will be chosen to be opaque and lined inside with carbon paper. Envelopes will be opened sequentially after writing the subject's tracking information on the envelope so that the carbon paper served as an audit trail. At the time of procedure, the

responsible investigator will open the envelope to reveal the assignment, and she will introduce the planned method.

After enrollment, the cases will be randomly allocated into two groups:

- **Group A(n=30):** Will be the case group, it includes cases who will receive Ulipristal Acetate plus Misoprostol.
- **Group B(n=30):** will be the control group, it includes cases who will receive Misoprostol only plus a structurally similar placebo drug manufactured at Ain Shams Pharmacology department.

Ethical Considerations:

The nature and scope of the clinical study will be explained in a form understandable to the patient and an informed consent document, in Arabic language, contains all locally required elements and specifies who informed the patient, will be provided and the patient must give written consent. Patients should be counseled that medication abortion takes longer and that they may have a greater awareness of blood loss and passage of pregnancy tissue with high risk of rupture uterus (0.3%)[16] and blood transfusion. The study protocol and patient informed consent will be reviewed and approved by the Ethics Committee of the Obstetrics and Gynecology Department Ain Shams University.

1. **NICE Clinical guideline 2012. Diagnosis and initial management in early pregnancy of ectopic pregnancy and miscarriage.**
2. **McNamee KM, Dawood F, Farquharson RG. Mid-trimester pregnancy loss.**
Obstet Gynecol Clinics North America 2014; 41(1):87–102.

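### A placebo is supplied, but the envelope step as written shows the arm to the responsible investigator, and neither document says who, if anyone, is blind

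*Protocol*

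**What the plan says.** Under Study Design the protocol gives only "Type of Study: A Randomized Controlled Trial", with no term for blinding or masking. Under Interventions, Group A "will receive Ulipristal acetate 30mg, starting misoprostol 12 hours later", and Group B "will receive placebo tablet then 12 hours later start misoprostol". The description of the groups adds that controls receive "Misoprostol only plus a structurally similar placebo drug manufactured at Ain Shams Pharmacology department".

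The section Randomization, Allocation and Concealment describes sequentially numbered, opaque, sealed envelopes, each "containing a 2-inch by 2-inch paper with a written code designating the assigned group". At the time of the procedure, the "responsible investigator will open the envelope to reveal the assignment, and she will introduce the planned method".

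Both arms then follow the same misoprostol sequence, "repeating the same sequence for two weeks unless there is excessive bleeding or infection. If failed, patient will proceed to hysterotomy". The primary outcome is "Induction-to-abortion interval time". The secondary outcomes are complete evacuation, side effects (nausea, vomiting, fever, pain), uterine rupture, blood loss and hysterotomy.

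The SAP lists software, tests and the significance level and is silent on blinding. Its mention of coding refers to the collected data, not to the treatment supply.

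**The concern.** The main reason to make a look-alike placebo is to keep people unaware of the arm. A step that discloses the arm to the person who starts treatment gives up much of that benefit. It also leaves the reader unable to tell whether the trial is double-blind, single-blind or open.

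This matters because several outcomes rest on judgement. Someone who knows the arm may expect the new drug to work. The pull may also go the other way. The protocol notes that ulipristal has not previously been used for this purpose, and every woman has a caesarean scar, so the ulipristal arm may be watched more closely, have more side effects recorded or be stopped sooner.

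Concealment of the sequence before assignment is well described and is not in question. It protects against selective enrolment. It does not protect care and assessment after the envelope is opened.

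**Working it through.** There is no figure in the plan to reproduce, and no calculation bears on whether anyone is blind. The check is a comparison of the relevant statements.

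1. **Is masking of the tablet provided for?** In part. A structurally similar placebo is made at the hospital's pharmacology department (Protocol, group descriptions). Nothing is said about identical packaging, coded labels or who dispenses.

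2. **Who learns the arm?** The envelope paper designates the group, and the responsible investigator opens it in order to reveal the assignment and then starts the method. The same section distinguishes intervention envelopes from control envelopes, which fits the plain reading.

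3. **Two readings of the code.**
   - The code identifies the arm. The responsible investigator is then not blind, although the woman and others may be.
   - The code is masked, for example a supply number. This would need tablets labelled by that code and someone outside patient care who holds the key. Neither is described, and the wording about revealing the assignment would then be wrong.

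   Under either reading the protocol text has to change.

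4. **Does any other statement settle it?** No. The design label, the intervention section and the SAP name no blinded party, blinded assessor, code holder or unblinding step.

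5. **Which outcomes are exposed if the arm is known?**
   - Complete evacuation and blood loss: most exposed, because staff judge or record them.
   - Side effects: fever can be measured. Nausea and pain are largely reported by the woman, so they are less exposed if she is blind.
   - Early stopping for bleeding or infection: exposed, because it is a judgement made during the two-week course.
   - Hysterotomy: follows a rule common to both arms, so it is exposed mainly through that same exception.
   - Primary interval: less exposed. Abortion is a discrete event, and both arms share the same 12-hour gap, misoprostol schedule and two-week rule.

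6. **Cost input.** Two groups of 30 give 30 + 30 = 60 containers at most.

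**The case against.** The strongest reply is that unblinding is not established. The paper carries a code, and a placebo made specially for the trial makes most sense if masking was intended. The protocol speaks of the responsible investigator and does not say that she manages the two-week course or judges any outcome. Title and consent pages are not in the text available, so a blinding label there cannot be excluded.

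Much of this stands. It limits the point to what the text shows and fails to show. It does not remove the point, because the operative instruction says that the assignment is revealed, and a label elsewhere would still have to be reconciled with that instruction.

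A reader might be tempted by stronger readings that the documents do not support:
- *The trial is open-label.* The text does not show that the women, ward staff or assessors know the arm.
- *Early stops distort the log rank comparison.* The SAP gives no censoring rule and does not tie that test to the primary interval. It also provides t and Mann-Whitney tests for quantitative data.
- *The 12-hour gap between tablet and misoprostol gives the size of the bias in the interval.* The gap is the same in both arms and cancels if one start point is used. Nothing suggests that start times were recorded differently by arm.
- *Undefined outcome criteria are part of this fault.* They would be the same gaps in a perfectly blinded trial and are a separate matter.

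**Conclusion.** The point holds in a limited form. As written, the envelope step shows the arm to the person who starts treatment and wastes a placebo that is already being made, and neither document establishes who is blind. The size and direction of any resulting bias cannot be estimated from the documents.

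The conclusion rests on the plain reading of the envelope instruction and on the absence of any statement about blinding in the protocol and SAP as supplied. If the code was in fact masked and the tablets were dispensed by that code, what remains is a gap in description. If the assignment was visible, the judged secondary outcomes and the early-stop decisions carry a risk of bias, to the extent that those who made them knew the arm. Randomisation itself is not undermined. The change should be made, but the point does not invalidate the trial.

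**What to change.** **If treatment has not yet been given.**
- The department that makes the placebo confirms that the two tablets look alike, or masks them so that they do.
- It packs ulipristal and placebo in identical, sequentially numbered containers in the order of the randomisation list, and holds the list and emergency code-breaks outside patient care until data lock.
- The envelope shows only the container number, or the container replaces it, and the wording about revealing the assignment is amended to match.
- The protocol states that patient, investigator, ward staff and outcome assessors are blind.

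The cost is a check of tablet appearance, packing up to 60 containers, and custody of the list. The women have no added visits or procedures.

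**If treatment is complete.** This is likely: the study period runs to January 2020, and the SAP is dated February 2020 and written in the past tense.
- Establish what the code showed and how tablets were dispensed.
- If both were masked, say so.
- If the assignment was visible, report the trial as not investigator-blinded, give early stops by arm with time and reason, and interpret the judged outcomes with caution. A later blinded re-reading of the records cannot remove bias already present in the source entries.

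The cost is one check of codes and dispensing and a few sentences of reporting.

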Efficacy of Ulipristal Acetate in Induction of Second Trimestric Missed Abortion in Women with Previous Caesarian section: Randomized Controlled Trial.

Document date : February 2020

Statistical analysis:

The collected data were coded, tabulated, and statistically analyzed using IBM SPSS statistics (Statistical Package for Social Sciences) software version 22.0, IBM Corp., Chicago, USA, 2013. Quantitative normally distributed data described as mean±SD (standard deviation) after testing for normality using Shapiro-Wilk test, then compared using independent t-test if normally distributed and Mann Whitney test if not normally distributed, while Pearson test was used for correlations. Qualitative data described as number and percentage and compared using Chi square test and Fisher's Exact test for variables with small expected numbers. Log rank test was used to compare abortion rate. The level of significance was taken at P value < 0.050 was significant, otherwise was non-significant
